10.0 CORRELATIVES/SPECIAL STUDIES

The goal of the planned laboratory correlative studies is to improve our understanding of the biological processes that drive GVHD and its clinical outcomes.

10.1 Sample Collection Guidelines

The correlative sample collection schedule is detailed in section 6.3 above. Serum will be collected in no additive, silicone coated glass or plastic tubes containing no anticoagulant (red or gold top tube). Samples will be processed at the participating center and batch shipped to [name] Laboratory quarterly for storage. Sample processing details are found in the appendices. Instructions for quarterly batch shipping are found in the MAGIC Sample Collection and Storage Manual.

10.2 Assay Methodology

See Appendix A.

10.3 Specimen Banking

Patient samples collected for this study will be stored indefinitely or until they are used up. If future use is denied or withdrawn by the patient, best efforts will be made to stop any additional studies and to destroy the specimens. In addition to the biomarker studies planned as part of this study, additional studies may be performed on the banked research samples as part of collaborations with other institutions and entities.

The specimens, DNA, and their derivatives may have significant therapeutic or commercial value. The Informed Consent form contains this information and informs the subject that there is the potential for financial gain by the Icahn School of Medicine at Mount Sinai, the investigator or a collaborating researcher or entity.

The following information obtained from the subject's medical record may be provided to research collaborators when specimens are made available:

- Diagnosis
- Collection time in relation to study treatment
- Clinical outcome if available
- Demographic data

11.0 STATISTICAL CONSIDERATIONS

11.1 Study Design/Study Endpoints

This is a non-inferiority, phase II, single arm, open-label, multicenter clinical trial to determine the effectiveness of itacitinib monotherapy as primary treatment of newly diagnosed, low-risk acute GVHD defined by standard risk clinical criteria (Minnesota) and low risk biomarkers (Ann Arbor 1). The primary study measure is the proportion of patients who achieve CR or PR by day 28 of treatment with itacitinib without the addition of any other systemic GVHD treatment including steroids. CR is defined as absence of GVHD symptoms. PR is defined as improvement in one or more organs involved with GVHD symptoms without progression in other organs. For a response to be scored as CR or PR on day 28, the patient must be in CR or PR on day 28 and have had no intervening systemic therapy for acute GVHD other than itacitinib.

To further investigate the treatment regimen, we will assess the safety of itacitinib monotherapy in these patients, determine the incidence of serious complications within three months in patients with GVHD treated with itacitinib and determine the incidence of steroid refractory GVHD in patients whose GVHD is not responsive to itacitinib (as defined in section 2.3) as secondary objectives. Secondary endpoints will include cumulative incidence of steroid-refractory GVHD, proportion of patients with maximal grade I, II, III,

and IV GVHD by day 28 after starting treatment with itacitinib, cumulative incidence of serious infections (defined as bacteremia needing treatment, CMV infection needing treatment, EBV infection needing treatment, or invasive fungal infection), overall survival at 6 and 12 months, cumulative incidence of NRM at 6 and 12 months, relapse rate, and cumulative incidence of chronic GVHD requiring systemic steroid treatment by one year.

As a safety endpoint, we will calculate number and proportion of patients developing reportable AEs and SAEs according to relatedness to study drug and stratified by severity.

Our exploratory hypotheses are as follows: 1) GVHD biomarkers (such as ST2 and REG3 α) will remain low in study patients who respond to itacitinib treatment, but will rise in non-responders. 2) biomarker concentrations will be equivalent to those in historical control patients who respond to steroid treatment for low risk GVHD. The historical control population for this study will be derived from MAGIC patients worldwide who enroll from 2014-2019. We expect at least 500 patients with Minnesota standard risk/Ann Arbor 1 GVHD will be available as control patients.

11.2 Sample Size and Accrual

In this phase II clinical trial, our aim is to determine if itacitinib monotherapy as primary treatment of newly diagnosed, low-risk acute GVHD defined by standard risk clinical criteria (Minnesota) and low risk biomarkers (Ann Arbor 1) is non-inferior to standard steroid therapy. The expected proportion of low-risk acute GVHD patients who achieve CR or PR by day 28 of standard steroid treatment is 67%. Avoidance of the toxicity of steroid treatment is a priority for the HCT community in general and MAGIC centers specifically. Extensive preliminary discussion indicate that physicians would accept a 15% decrease in the overall response rate to primary GVHD treatment (from 67% to 52%) if steroid treatment could be avoided in the responders without an increase in the incidence of steroid refractory GVHD. This study will terminate early if the incidence of steroid refractory GVHD exceeds the historical rate of 33%, if the incidence of serious infections exceeds the historical rate of 59% or if the incidence of non-relapse mortality (as a measure of all potential toxicities) exceeds the historical rate of 9% (section 8.7).

A one-sided group sequential design that uses O'Brien-Fleming method testing an upper (futility) stopping boundary is used to stop the trial early for futility. Two equally spaced formal interim analyses will be performed during the monitoring of the study. Under such a monitoring schedule and assuming a baseline 28-day response rate of 0.67 in standard steroid treatment, a sample size of 70 patients will provide 80% power to detect a non-inferiority margin of 0.15 in response rate by day 28. Under the planned schedule of two equally spaced analysis and assuming a baseline response rate of 0.67, the table below presents the stopping boundaries at each analysis for the specified stopping rule expressed as the number of responses by day 28.

Stage	Sample Size	Futility stopping boundary	
_		Z statistic	Number of CR and PR
			by day 28
1	35	0.558	19
2	70	1.734	44

According to the above table, if at first analysis the response rate by day 28 is less than or equal to 19, the stopping rule suggests that the study be terminated early with a decision that it was futile to continue the trial because there is not sufficient evidence that any beneficial effect of the experimental treatment is clinically important.

The combination of the primary efficacy endpoint (overall response rate) and the secondary endpoints (steroid-refractory GVHD, NRM, and serious infections) will be used to

determine if itacitinib monotherapy should be compared to systemic steroid treatment in a phase III trial for patients with low risk GVHD. We will continuously monitor these outcomes and if at any point during this trial sufficient evidence emerges that itacitinib monotherapy is not likely to result in improvement in any of these parameters, the protocol committee will terminate the trial for futility.

Sample size calculations were performed using seqdesign statement in PASS 14 Power Analysis and Sample Size Software (2015) NCSS, LLC. Kaysville, Utah, USA, ncss.com/software/passSAS software version 9.4 (SAS Institute Inc., Raleigh, NC).

The centers participating in this clinical trial collectively perform >700 allogeneic HCT per year. Based on data from these MAGIC centers from 2013-2017, we expect 300 patients will develop GVHD per year, including 255 with Minnesota Standard Risk GVHD. Although it is likely we will accrue faster, a conservative estimate is that we will consent and screen 50% of these cases which should result in 48 patients enrolled per year or approximately 4 per month. We do not expect all centers to open to enrollment simultaneously and therefore we realistically expect to meet our accrual goals within two years.

11.3 Data Analysis Plans

The primary endpoint is the proportion of patients who achieve CR or PR by day 28 of treatment with itacitinib without the addition of any other systemic GVHD treatment including steroids. Death, lack of GVHD response to itacitinib by day 28 of treatment, or initiation of steroid or other systemic immunosuppressive therapy for GVHD will be considered failures for this endpoint. The proportion of patients who achieve CR or PR by day 28 in the study patients will be compared to the historical control rate of 67%.

Secondary outcomes such as cumulative incidence of steroid-refractory GVHD, proportion of patients with maximal grade I, II, III, and IV GVHD by day 28 after starting treatment with itacitinib, cumulative incidence of serious infections, cumulative incidence of hematologic toxicities, cumulative steroid dose over four weeks in patients who fail itacitinib monotherapy, overall survival at 6 and 12 months, cumulative incidence of NRM at 6 and 12 months, relapse rate at 6 and 12 months, and cumulative incidence of chronic GVHD requiring systemic steroid treatment by one year will be estimated and compared to historical controls.

Continuous variables will be summarized using standard summary statistics such as number of observations (n), mean, standard deviation (SD), minimum and maximum values, median, and 1st and 3rd quartiles. Categorical variables will be summarized in frequency tables as counts and percentages.

Cumulative incidence of non-relapse mortality will be estimated by Gray's method⁵³ and relapse will be considered as a competing risk. Disease free and overall survival, defined as the time from the transplantation to death or to last follow-up if alive, will be estimated by the method of Kaplan-Meier and the probability curves and 95% confidence intervals will be provided based on the method of Brookmeyer and Crowley⁵⁴.

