Statistical Methodology	The primary study measure is the proportion of patients who achieve CR or PR by day 28 of treatment with itacitinib without the addition of any other systemic GVHD treatment including steroids. The expected proportion of low-risk acute GVHD patients who achieve CR or PR by day 28 of standard steroid treatment is 67%. Extensive preliminary discussion indicate that physicians would accept a 15% decrease in the overall response rate to primary GVHD treatment (from 67% to 52%) if steroid treatment could be avoided in the responders without an increase in the incidence of steroid refractory GVHD. A sample size of 70 achieves 81% power to detect a non-inferiority proportion of 52% using a one-sided exact test with a significance level of 0.04 calculated using binomial enumeration of all possible outcomes. This study will terminate early if the incidence of steroid refractory GVHD exceeds the historical rate of 38% or if the incidence of non-relapse mortality (as a measure of all potential toxicities) exceeds the historical rate of 9% (section 8.7).

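### Section 11.3 compares the primary response rate only with 67% and omits the 52% non-inferiority limit, and the plan never says whether exactly 44 of 70 is success

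*Combined protocol and SAP*

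**What the plan says.** The synopsis (Statistical Methodology) gives the power as follows: "A sample size of 70 achieves 81% power to detect a non-inferiority proportion of 52"%. It names the method as a "one-sided exact test with a significance level of 0.04 calculated using binomial enumeration of all possible outcomes". It mentions no interim look at response.

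Section 11.1 sets the design type: "This is a non-inferiority, phase II, single arm, open-label, multicenter clinical trial". Section 11.2 gives the reason for the limit, that "physicians would accept a 15% decrease in the overall response rate to primary GVHD treatment (from 67% to 52"%), and claims "80% power to detect a non-inferiority margin of 0.15 in response rate by day 28" for 70 patients under a group sequential futility design. It states no alpha. Its table has two rows: 35 patients, Z 0.558, 19 responses; and 70 patients, Z 1.734, 44 responses. Both rows stand under a heading for a futility boundary. The text explains only the first row: at 19 or fewer, the rule suggests stopping.

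On the number of looks, 11.2 first says "Two equally spaced formal interim analyses will be performed during the monitoring of the study". It then introduces the table with "Under the planned schedule of two equally spaced analysis and assuming a baseline response rate of 0.67".

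Section 11.3 says of the primary comparison only that the proportion responding "in the study patients will be compared to the historical control rate of 67"%. For this endpoint it gives no margin, no 52%, no test, no level and no confidence bound.

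**The concern.** Section 11.3 is where an analyst looks for the primary comparison. It names the rate from which the margin is taken but not the limit on which the decision turns. The limit has to be fetched from the synopsis or 11.2.

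The final count is also not settled in words. If the explanation of row 1 is carried down to row 2, 44 responses is a failure and success starts at 45. If 44 is the critical value of the final test, 44 is a success. A trial that ends with exactly 44 responders would be decided by whoever interprets the table.

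Finally, the synopsis describes a single-stage test and 11.2 a design with a futility look. A reader cannot tell which of the stated operating characteristics belong to the trial that will be run.

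**Working it through.** **Inputs.** N = 70, limit p0 = 0.52, expected rate p1 = 0.67, one-sided level 0.04, power 81% (synopsis). Look at 35 with a stop at 19 or fewer, final Z 1.734 and count 44, power 80% (11.2).

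**Step 1: reproduce the synopsis.** For a single stage with success at c or more responses, alpha = P(X ≥ c | 70, 0.52) and power = P(X ≥ c | 70, 0.67).

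| c | alpha | power |
|---|---|---|
| 43 | 0.0717 | 86.8% |
| 44 | 0.0440 | 80.7% |
| 45 | 0.0257 | 73.2% |

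The row c = 44 reproduces 81%. It reproduces 0.04 only as an attained level rounded to two decimals.

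**Step 2: add the look at 35.** With a stop at 19 or fewer, P(success) = Σ over x1 = 20 to 35 of P(X1 = x1 | 35, p) × P(X2 ≥ c − x1 | 35, p).

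| c | alpha | power |
|---|---|---|
| 44 | 0.0409 | 78.6% |
| 45 | 0.0245 | 71.9% |

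The chance of stopping at the look is 0.669 at a true 52% and 0.080 at a true 67%.

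**Step 3: compare with the 80% in 11.2.** The table is on a Z scale, so a normal calculation is the fair comparison. With boundaries 0.558 and 1.734, power is 79.4% with the variance taken at 67% and 74.9% with it taken at 52%. The one-sided normal tail beyond 1.734 is 0.0415, or 0.0373 if the futility stop is binding. The 80% is therefore close to the normal result, and most of its distance from 78.6% is approximate versus exact calculation.

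**Step 4: which way does 44 point?** Convert Z to a count: n × 0.52 + Z × √(n × p × (1 − p)), with p for the variance set at 0.52 or 0.67.

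- Row 1: 18.2 + 0.558 × √(35 × 0.52 × 0.48) = 19.8. With the variance at 0.67 it is also 19.8.
- Row 2: 36.4 + 1.734 × √(70 × 0.52 × 0.48) = 43.6. With the variance at 0.67 it is 43.2.

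The boundary in row 1 lies just above 19, so 19 is the last count that stops. The boundary in row 2 lies between 43 and 44, so 44 is the first count that passes. The two rows are printed under one heading but point in opposite directions.

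**Step 5: matching confidence bound.** The one-sided 95% exact lower bound is 50.9% at 43/70 and 52.4% at 44/70, so it gives the same rule as success at 44 or more. The 96% bound is 51.7% at 44/70 and 53.2% at 45/70, so it goes with 45 or more.

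None of these figures includes the safety stopping rules of section 8.7.

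**The case against.** The strongest reply is that the design is recoverable. The synopsis gives the test, side, level and limit in words, 11.2 repeats the margin, and 11.1 says non-inferiority. A non-inferiority trial does compare with its control rate, so naming 67% in 11.3 leaves the statement incomplete without creating a rival test. All of this stands. It confines the gap to the missing limit in 11.3 and the unstated meaning of 44.

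A reader might infer more from 11.3. Taken as superiority over 67% at 0.04, it would need 55 of 70 (attained 0.0237) and would succeed 2.4% of the time at a true 67%. Taken as not significantly below 67% at 0.04, it would pass from 40 of 70, since P(X ≤ 39 | 0.67) = 0.0320. The documents support neither reading. The synopsis, 11.1 and 11.2 all describe non-inferiority, with a limit of 52%, and no section states either rule. These counts do not measure the impact of the gap.

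A reader might also infer that 0.04, 81% and 44 cannot belong to one design. They can: step 1 shows all three in a single-stage test, if 0.04 is a rounded attained level. What remains is that this design lacks the look that 11.2 plans.

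The count of two interims is probably a slip, because the later sentence and the table both show two analyses in all. It still contradicts the table.

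**Conclusion.** The point holds as a fault of specification. Section 11.3 omits the 52% limit, no section says whether 44 of 70 passes, the synopsis figures ignore the planned look, and the stated number of interims contradicts the table.

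The one consequence of real size is the meaning of 44: with the look, power is 78.6% if it passes and 71.9% if it fails, a difference of 6.7 points. The printed Z supports passing, but that is an inference from the table. The other gaps are small: 78.6% against a stated 80% or 81%, and attained alpha of 0.0409 (0.0440 if the futility stop is overridden) against 0.04. They do not show that the sample size or either boundary is wrong.

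The figures assume independent responses, a true rate of 67% for power, exact binomial calculation, a stop at 19 or fewer of 35, and no stop under section 8.7. If 0.04 is a strict limit, 44 exceeds it with or without the look, and the cut-off becomes 45.

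**What to change.** 1. In 11.3, state H0: p ≤ 0.52 against H1: p > 0.52, with non-inferiority declared at 44 or more responses in 70. The sponsor should confirm that count. Keep 67% as the rate from which the 15-point margin is taken.
2. In the 11.2 table, label 19 as stop if this many or fewer, and 44 as success if this many or more.
3. Replace the two interim analyses with one interim (35) and one final analysis (70).
4. Describe this same design in the synopsis and 11.2. Give attained exact alpha of about 0.041 and power of about 79% if the futility stop is followed, or 0.044 and 80.7% if it is overridden. Say whether the stop binds, since 11.2 words it as a suggestion, and note that the figures exclude the section 8.7 rules.
5. If 0.04 is meant as a strict limit, print 45 as the success count and 71.9% as the power with the look.
6. Match any reported one-sided bound to the choice: 95% goes with 44 or more. A 96% bound does not.

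With 44 as success, the sample size and printed boundaries stay as they are. The cost is that stated power falls by 1 to 2 points and stated alpha is slightly above 0.04. Whether 44 passes, whether 0.04 is strict and whether the futility stop binds are the sponsor's design choices and need an explicit decision.

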3.1 Inclusion Criteria

- 3.1.1 Newly diagnosed GVHD that meets criteria for Minnesota standard risk (see section 7.0)
- 3.1.2 Ann Arbor 1 GVHD by biomarkers
- 3.1.3 GVHD not previously treated systemically (topical therapies and non-absorbed steroids are allowed)
- 3.1.4 Any donor type, HLA-match, conditioning regimen is acceptable
- 3.1.5 Age 12 years and up (children <18 years must weight 50 kg or more)
- 3.1.6 Patients must be engrafted post-transplant (ANC ≥500/µL and platelet count ≥20,000). Use of growth factor supplementation to maintain neutrophil count is allowed.
- 3.1.7 Direct bilirubin must be <2 mg/dL unless the elevation is known to be due to Gilbert syndrome within 3 days prior to enrollment.
- 3.1.8 ALT/SGPT and AST/SGOT must be <5x the upper limit of the normal range within 3 days prior to enrollment.
- 3.1.9 Signed and dated written informed consent obtained from patient or legal representative.

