6.0 STUDY PROCEDURES

6.1 Screening/Baseline Procedures

Assessments performed exclusively to determine eligibility for this study will be done only after obtaining informed consent. Assessments performed for clinical indications (not exclusively to determine study eligibility) may be used for baseline values even if the studies were done before informed consent was obtained. Frequent monitoring of clinical chemistry and hematology is routine in HCT patients. This study does not require specific laboratory monitoring other than specified below.

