6.1.6 Serum chemistries (within 3 days prior to enrollment)

ALT/SGPT, AST/SGOT, and total bilirubin are required for assessment of exclusion criteria within 3 days prior to enrollment.

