7.2.2 Hematologic Toxicities

Hematologic toxicities will be graded according to CTCAE v4 criteria.

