also be possibly, probably, or definitely related to itacitinib. After 30 days from the last dose of itacitinib, adverse events should only be reported if they are both serious and probably or definitely related to itacitinib. Events that are unlikely or unrelated to itacitinib are not required to be reported. Reporting of such events should include the investigator's assessment as to whether the event should be attributed to any of the HCT procedure itself, GVHD, exposure to immunosuppressive agents other than itacitinib, and itacitinib. An event may be attributable to all, some, or one of these categories.

• Abnormal laboratory values or test results constitute adverse events only if they induce clinical signs or symptoms or require therapy and otherwise meet the criteria for a reportable adverse event as defined above. They are to be captured under the signs, symptoms or diagnoses associated with them.

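### Hematologic toxicity is a planned outcome, but no on-treatment blood counts are recorded and asymptomatic, untreated cytopenias need not be reported, so its incidence is expected to read low

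*Combined protocol and SAP*

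**What the plan says.** Section 11.3 names "cumulative incidence of hematologic toxicities" among the secondary outcomes that "will be estimated and compared to historical controls". Section 7.2.2 adds one sentence: "Hematologic toxicities will be graded according to CTCAE v4 criteria". Neither place gives a grade threshold, a time window, a competing event or a historical rate.

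On data collection, section 6.1 notes that "Frequent monitoring of clinical chemistry and hematology is routine in HCT patients" and then says "This study does not require specific laboratory monitoring other than specified below". What follows is section 6.1.6: "ALT/SGPT, AST/SGOT, and total bilirubin are required for assessment of exclusion criteria within 3 days prior to enrollment". The Time and Events Table under section 6.2 has a single laboratory row, serum chemistry, marked at screening only.

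On reporting, section 8.3.1 states: "Abnormal laboratory values or test results constitute adverse events only if they induce clinical signs or symptoms or require therapy". The abnormality must also meet the other reporting criteria, and grade 1 and 2 events are generally not reported. The same section says that symptoms of the underlying disease are not adverse events, with an exception for hematologic toxicities that it promises to define further on. No definition follows.

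**The concern.** A cumulative incidence of graded cytopenia needs dated counts: a baseline, repeated values, and the date at which a threshold is crossed. The plan schedules none of these. It relies on adverse event reports, which pass through a filter based on symptoms or treatment rather than on the laboratory grade. CTCAE grading of the counts and the section 8.3.1 rule can therefore give different numbers for the same patients.

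The outcome bears on the rationale for the drug. Section 1.4 presents cytopenia as the main complication of ruxolitinib and as the reason for developing a more selective JAK1 inhibitor. Section 5.3 reports a roughly 5-fold rise in itacitinib exposure with a strong CYP3A4 inhibitor and recommends monitoring hematology in that case, but nothing in the plan records the result. A low reported incidence could be read as confirming the rationale when it partly reflects what was not written down.

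**Working it through.** **1. What is recorded.**
- *Post-baseline counts.* None is scheduled. Routine care will produce counts, but no passage tells sites to enter them.
- *Baseline.* Section 3.1.6 requires an ANC of at least 500/µL and platelets of at least 20,000, allows growth factor to maintain the neutrophil count, and sets no time window. Section 8.2 treats laboratory abnormalities with onset before first dose as pre-existing. Without a dated day-0 count, new and pre-existing cytopenia cannot be separated reliably.
- *Treatment of cytopenia.* Section 6.1.4 and footnote 2 of the Time and Events Table limit medication review to immunosuppressants and drugs for GVHD prevention or treatment. Growth factor and transfusions are not scheduled data, so reports made under the therapy limb of section 8.3.1 cannot be checked against them.

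**2. What the reporting rule keeps.** For a grade 3-4 cytopenia under section 8.3.1:

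| | Treated | Not treated |
|---|---|---|
| Symptomatic | reportable | reportable |
| Asymptomatic | reportable | not an adverse event |

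Only the last cell drops out. The filter removes events and adds none, so the absolute incidence can only be at or below the laboratory-based figure.

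**3. The plan's background rates.** The monotherapy table in section 9.1 gives these grade 3-4 counts, with percentages on the 209 subjects with underlying disease:
- Anemia: 26/209 = 12.4%
- Thrombocytopenia: 19/209 = 9.1%
- Neutropenia: 3/209 = 1.4%

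These match section 7.2.1 and the pooled line in section 9.1. That line is labelled n=777, but on 777 the rates would be 3.3%, 2.4% and 0.4%.

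**4. Illustration of size.** Reported incidence = true incidence × capture share. The documents do not give the capture share; 0.2 to 1.0 is an assumption. With n = 70:

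| True rate | Share 0.2 | Share 1.0 |
|---|---|---|
| 12.4% | 0.124 × 0.2 = 2.5% (1.7 patients) | 12.4% (8.7 patients) |
| 9.1% | 0.091 × 0.2 = 1.8% (1.3 patients) | 9.1% (6.4 patients) |

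The true rates are borrowed from a different population, in which section 7.2.1 says these events were most common in myelofibrosis. They set a scale and are not a forecast.

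**The case against.** The best defence is that other passages point towards capture. Section 7.2.1 says that known or plausible itacitinib toxicities will be reported, directly after discussing hemoglobin, platelets and neutrophils. Section 8.3.1 includes abnormal laboratory findings in its general definition of an adverse event, and section 8.2 requires events of grade 3 or higher on the CRF. ANC and platelets are checked for eligibility, and source documents go to the coordinating center. The CRFs are not in these documents and might hold counts. This stands to the extent that the text is in conflict rather than a settled exclusion. It does not remove the filter in section 8.3.1, supply the missing definition, or add a count to the schedule.

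The consequence is also limited. The outcome is absent from the endpoint lists in sections 2.3 and 11.1, from the stopping rules in section 8.7, and from the outcomes that section 11.2 uses to decide on phase III.

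A reader might infer more than the documents support:
- *That every asymptomatic cytopenia is lost.* Treated ones remain reportable.
- *That about 90% of events would be missed*, because only 5 of 26 + 19 + 3 = 48 grade 3-4 entries in the section 9.1 table were serious (10%). Seriousness is not the capture rule during treatment, and the 48 may count one subject several times.
- *That the 41.4% thrombocytopenia rate in the earlier GVHD study shows the expected burden.* It covers all grades, with concurrent steroids, and 10 of the 12 cases were at 300 mg. At 200 mg it was 2/14 (14.3%).
- *That the comparison must favour itacitinib.* The documents do not say how cytopenia was ascertained in the controls.

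**Conclusion.** The planned outcome and the planned data do not fit together. Followed as written, asymptomatic and untreated grade 3-4 cytopenias need not be recorded, and the absolute incidence is expected to be biased low relative to laboratory-based CTCAE grading. That direction rests on two readings: that sites apply section 8.3.1 literally, and that no CRF outside these documents collects counts.

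The size cannot be computed from the documents, and the range of 2.5% to 12.4% holds only under the assumed capture share. The direction of bias in the historical comparison is unknown. The safety conclusion is affected; the primary endpoint, the stopping rules and the phase III decision set are not. The change is worth making because it is cheap, but the trial's main result does not depend on it.

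**What to change.** 1. Add a row to the Time and Events Table for transcribing dated hemoglobin, platelets and ANC from the routine blood count nearest day 0 and each existing GVHD staging visit through day 90.
2. Reconcile sections 7.2.2, 8.3.1 and 11.3 with one definition: new or worsened grade 3-4 cytopenia relative to the day-0 grade, within a stated window, with death as a competing event, counted whether or not symptomatic or treated. State how patients already at grade 3-4 on day 0 are handled, and whether counts after itacitinib stops are included.
3. In section 8.3.1, either supply the definition that the exception promises or refer to the new one, and exempt this outcome from the symptom-or-therapy filter.
4. In section 11.3, name the source of the historical rate. Compare only if control counts were ascertained in the same way; otherwise report the incidence descriptively.

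The cost is data entry: 3 values at 8 visits (days 0, 7, 14, 21, 28, 42, 56 and 90) for 70 patients is at most 3 × 8 × 70 = 1,680 values, taken from tests that section 6.1 describes as routine. No procedure is added. The reported toxicity rate is likely to look less favourable.
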